21 STUDY ASSESSMENTS

21.1 Demographics

At Visit 1 the following information will be collected and registered in the CRF: age, height, weight, BMI, gender and ethnic origin.

21.2 Clinical efficacy assessments

1. Gastrointestinal and Colonic Transit

An adaptation of our established scintigraphic method will be used to measure gastrointestinal and colonic transit. Briefly, ¹¹¹In absorbed on activated charcoal particles is delivered to the colon by means of a methacrylate-coated, delayed-release capsule. The capsule is ingested following an overnight fast. Colonic transit measurements will be performed by means of the delayed release capsule. After the capsule emptied from the stomach (documented by its position relative to radioisotopic markers placed on the anterior iliac crests), the study medication is given immediately before a standard radiolabeled breakfast meal is ingested. In this meal, ^{99m}Tc-sulfur colloid is used to label two scrambled eggs that will be eaten with one slice of whole wheat bread and one glass of skim milk. This meal facilitates measurement of gastric and small bowel transit.

Relative to the time of consumption of breakfast meal, abdominal camera images are initially obtained every 30 minutes for the first two hours, then hourly for the next six hours. At about 4 hours, a standard chicken breast lunch will be given. Camera images will be taken at 5, 6, and at 8 hours post breakfast meal. At about 8 hours, the standard roast beef sandwich snack will be given. The patient will leave the CRU after the completion of the 8 hour image and will return the following two mornings in order to receive study medication and obtain 24 and 48 hour scans fifteen minutes later. The performance characteristics of this test are summarized elsewhere. Please see relevant references on the methods (29,30).

2. Assessment of stool frequency and consistency

During the study, patients will complete a daily Bowel Pattern Diary to record their bowel habits. The Bowel Pattern Diary will be dispensed at Visit 1 and will be collected at the completion of the study at Visit 7.

- 3. Pharmacokinetic (PK) and pharmacodynamic (PD) assessments
- a. Sample collection and handling

Blood samples for analysis of PK parameters will be collected at Visit 4, before dosing and at 30, 60, 90, 120, 180, 240, 360 and 480 minutes post-dose. One solitary sample to measure a baseline level at Visit 1 and one sample to measure a post treatment level at Visit 7 will be obtained. The samples will be drawn from an IV line into a lavender EDTA collection tube, centrifuged at 3000 rpm for 15 minutes and the plasma transferred to an anonymized polypropylene tube labeled only with a study number and patient initials as identifiers. The samples will be frozen at -70 degrees Celsius until they are batch shipped to Covance UK for analysis after the end of the study. One 5-mL pharmacodynamic sample to determine levels of C4 is taken at Visit 1, 4 and 7 and stored in the refrigerator for 30-60 min and thereafter serum is separated by centrifugation. The serum obtained is aliquoted into a cryo tube equipped with a screw-cap lid with a rubber o-ring. Samples are thereafter frozen at -70 degrees Celsius until they are batch shipped to Karolinska Institue, Sweden for analysis after end of the study. The total amount of blood drawn for these pharmacokinetic and pharmacodynamic samples is about 75 mL.

b. Pharmacokinetic analysis

PK parameters will be analyzed using conventional analyses by Covance, UK:

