- 2. A double-blind, randomized, placebo-controlled, phase Ib, dose-escalating study to assess the safety, tolerability and systemic exposure of A3309 capsules after repeated once daily administration to patients with chronic idiopathic constipation (Study A3309-001). Eligible patients should have had at least a 12 month history of constipation (defined as < 3 BMs per week) with symptoms and no more than 5 spontaneous complete bowel movements (SCBMs) during the 14 days preceding randomization. The initial screening evaluation included flexible sigmoidoscopy, colon transit measurement and a 14 day period to evaluate frequency of BMs and to calculate baseline data for GI symptoms. The primary objective of this study was to assess the safety and tolerability of A3309 after repeated oral doses to patients with chronic idiopathic constipation (CIC). Secondary objectives of the study were to assess: 1/ changes in (SCBM) and Bristol Stool Form score after repeated oral doses of A3309, 2/ to investigate colon transit and systemic availability of A3309 during escalating oral repeated doses and 3/ to evaluate the effect of A3309 by analysis of plasma glucose or HbA1c, triglycerides (TG), plasma lipid parameters. FGF19, FGF21 and C4. Patients were randomized in a 5:1 ratio to receive one of five sequential dose levels (0.1 mg, 0.3 mg, 1.0 mg, 3.0 mg or 10 mg) of A3309 or placebo, orally administered. A blinded safety assessment was performed between each dose level. The safety evaluation do not indicate any apparent effects on physical examination findings, vital signs, safety laboratory or 12-lead ECGs and no serious adverse events were reported. In 25 constipation patients, the adverse events observed were: abdominal distension, nausea and headache (8 percent each). The small number of subjects and events do not permit conclusions about any difference between groups in the nature, severity or incidence of adverse events. No deaths were reported and no adverse events led to treatment or study discontinuation. Pharmacokinetics: A3309 was detected in plasma in the picomolar range at doses of 1-10 mg. The highest individual levels at 10 mg were 0.33-0.76 nmol/L, seen 2 hours after 14 days of treatment. Cmax occurs within 4 h after dose. There is no obvious accumulation of neither A3309 or any metabolite since there were no detectable levels 24 hours after dose. The pharmacodynamic analyses provided evidence of biological activity consistent with the mechanism of action of A3309:

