⁹Criteria for randomization is defined as a geometric center < 2.30 at 24h, the median of normal colonic transit in normal healthy volunteers (as determined by analysis of a compilation of prior [name] studies)

¹⁰Blood samples for pharmacokinetics are obtained at Visit 4 at pre-dose, 30, 60, 90, 120, 180, 240, 360, 480 minutes after study medication. One blood sample for pharmacokinetics is obtained at Visit 1 and Visit 7 as well.

at this time. Height, weight and vital signs including temperature, pulse, blood pressure, and respiration rate will be obtained.

Blood and urine samples will be obtained to perform standard laboratory safety tests including a CBC, CMP, coagulation studies, UA, urine screen for drugs of abuse and a urine pregnancy test for females of childbearing potential. Note that females who are status post bilateral tubal ligation, hysterectomy or postmenopausal are exempted from this test. Blood samples will also be obtained for pharmacodynamics (C4, total cholesterol, LDL, HDL, and triglycerides) and one solitary pharmacokinetic sample. The total amount of blood obtained for the standard laboratory tests is about 30 mL. A 12-lead ECG will be performed.

Patients will review the study instructions and schedule with the study coordinator. The Long Bowel Disease Questionnaire (BDQ) will be completed to confirm patients have functional constipation. The Bowel Pattern Diary will be dispensed and reviewed.

Prior to Visit 2

Females of child bearing potential must have a negative urine pregnancy test performed within forty-eight hours prior to receipt of radiation in the abbreviated transit scintigraphy test. Females who have experienced a bilateral tubal ligation, hysterectomy or menopause will not need the pregnancy test.

Visit 2 Abbreviated Transit Scintigraphy

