The following morning, patients will return to the Charlton 7 CRU fasting for the previous eight hours, no food or drink allowed, to receive the study medication followed by one five minute camera image. A brief physical exam will be performed by a study physician. Patients may defer the rectal exam if not clinically indicated. Vital signs (pulse, blood pressure, respiration rate and temperature) will be measured. Patients will be asked about adverse events and concomitant medications by the study staff and the CRU nurses. Patients will complete a six question survey of constipation symptoms and treatment efficacy.

Visit 7 Study Completion

Within seven to ten days after Visit 6, patients will return to Charlton 7 CRU fasting for the previous eight hours, no food or drink allowed. Height, weight and vital signs (pulse, blood pressure, respiration rate and temperature) will be measured. Blood and urine samples will be obtained to perform standard laboratory safety tests including a CBC, CMP, coagulation studies and urinalysis. Blood samples will also be obtained for pharmacodynamics (C4, total cholesterol, LDL, HDL, and triglycerides) and one solitary pharmacokinetic sample. The total amount of blood obtained for the standard laboratory tests is about 30 mL. A 12-lead ECG will be performed. The Bowel Pattern Diary will be turned in. A physical exam will be performed by the study doctor; the patients may defer the rectal exam if not clinically indicated. An exit interview will be done with study staff.

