13 INCLUSION CRITERIA

- 1. Females aged 18 to 65 years old inclusive
- 2. An adaption of Rome II criteria for functional constipation will be used. Eligible patients must have functional constipation for the previous three months with symptom onset at least six months prior to diagnosis with less than three complete spontaneous bowel movements per week with two or more of the following:
 - a. hard or lumpy stools at least 25 % of the time
 - b. straining during a bowel movement at least 25 % of the time
 - c. sensation of incomplete evacuation at least 25 % of the time
 - d. sensation of anorectal obstruction/blockage at least 25 % of the time
- 3. A normal rectal exam result on file within the past 2 years or performed at Visit 1 screen by a qualified gastroenterologist to exclude the possibility of an evacuation disorder. Examination must exclude findings suggestive of an evacuation disorder such as high sphincter tone at rest, failure of perineal descent and spasm, tenderness or paradoxical contraction of the puborectalis muscles.
- 4. Females of child-bearing potential (those who have not experienced a bilateral tubal ligation, hysterectomy or menopause) must use an acceptable method of contraception during the study. Acceptable methods are surgical sterilization, hormonal methods such as oral contraceptives, Norplant and Depo-Provera, double barrier method such as a condom and spermicide, and an IUD. Abstinent females may participate if they agree to use the double barrier method should they become sexually active during the study.
- 5. Able to provide written informed consent prior to any study procedures being performed

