20.5 Treatment Compliance

Treatment compliance of greater than 80% is required and will be assessed by the patient's record of dosing contained in the Bowel Pattern Diary.

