24.6 Stool frequency and stool consistency

Patients are asked to keep a daily bowel pattern diary documenting the number of stools and the consistency (Bristol Stool Scale (28)) of each stool. These are averaged as number of bowel movements or consistency of bowel movements per day per patient. Number of bowel movements and consistency are subsequently averaged over the study periods (i.e. run-in and treatment) per patient. The ANCOVA will be used to assess treatment effects on each of these two measures separately, using the corresponding run-in values as covariates. In addition, treatment effects on specific constipation symptoms, considered as discrete categorical responses, will be evaluated by a contingency table analysis of the post-treatment responses based on the final post-treatment bowel pattern diaries and questionnaires concerning constipation symptoms and treatment efficacy.

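### The run-in diary pages that supply the baseline covariate stay with the patient until Visit 7; secure them at Visit 3, before the first dose

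*Combined protocol and SAP*

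**What the plan says.** Four places in the protocol agree on how the diary is handled. Section 21.2, item 2, says: "The Bowel Pattern Diary will be dispensed at Visit 1 and will be collected at the completion of the study at Visit 7". The Visit 7 text in 11.3 says: "The Bowel Pattern Diary will be turned in". Table 5 in 11.2 and the flow chart in 34.1 show the diary going out at Visit 1 and coming in at Visit 7, with nothing between.

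The only review mentioned is at Visit 1, when the diary is still empty: "The Bowel Pattern Diary will be dispensed and reviewed". The Visit 2 to Visit 6 texts in 11.3 include no diary check, copy or collection.

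The run-in pages have a statistical role. Section 24.6 averages stool frequency and consistency over run-in and treatment, and compares the arms by ANCOVA "using the corresponding run-in values as covariates". Section 24.1 also lists mean ease of passage among the diary summaries, each with its own baseline as a candidate covariate.

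The diary is also the stated source for compliance, through the patient's "record of dosing contained in the Bowel Pattern Diary" (20.5).

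**The concern.** ANCOVA adjustment relies on a baseline that treatment cannot have influenced. Here the baseline is a patient-held record that remains open to change throughout treatment. Section 12.2 expects effects a patient may notice: relief of constipation, possibly with diarrhea, gas and bloating. A patient who fills a blank run-in day in week two, or revises an earlier entry, does so knowing how she has felt since dosing began. If that happens differently by arm, the covariate carries part of the treatment effect, and adjusting for it distorts the estimate.

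There is also a plainer risk. A diary lost during treatment takes the baseline with it, and blank run-in days come to light only when they can no longer be recovered. With 12 patients per arm, each lost baseline counts.

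The protocol protects the other patient-reported baseline: the six-question survey is completed at Visit 3 before any study medication (11.3). The diary baseline has no such step. Section 23.3 does not name the diary among the source documents.

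**Working it through.** The plan gives no figure for this point, so there is none to reproduce. Two things can be worked out.

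**1. How long the pages stay open.** Inputs, from 11.2 and 11.3: Visit 2 is 7–14 days after Visit 1; Visit 3 is 0–3 days after Visit 2; Visits 4–6 fall on dosing days 12–14; Visit 7 is 7–10 days after Visit 6. Assumption: the first dose is on the day of Visit 3.

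- Run-in, Visit 1 to Visit 3: 7 + 0 = 7 days to 14 + 3 = 17 days.
- Visit 3 (day 1) to Visit 6 (day 14): 13 days.
- Visit 3 to Visit 7: 13 + 7 = 20 days to 13 + 10 = 23 days.

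The run-in pages therefore stay with the patient through all 14 doses and the whole follow-up. A first dose on the next day would add one day.

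**2. What differential late entry could do to the estimate.** Let δ be the true treatment effect on a diary measure, b the within-group slope of the outcome on baseline (equal variances), and c the between-arm shift in recorded baseline caused by late entry, as a fraction of δ. The adjusted difference is

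δ − b × (cδ) = δ(1 − bc).

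Neither b nor c is in the documents; both are assumptions shown over a range. The table gives the adjusted effect as a multiple of the true effect.

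| b | c = −0.5 | c = −0.25 | c = 0 | c = 0.25 | c = 0.5 |
|---|---|---|---|---|---|
| 0.3 | 1.15 | 1.075 | 1.00 | 0.925 | 0.85 |
| 0.5 | 1.25 | 1.125 | 1.00 | 0.875 | 0.75 |
| 0.7 | 1.35 | 1.175 | 1.00 | 0.825 | 0.65 |

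For example, b = 0.5 and c = 0.5 give 1 − 0.5 × 0.5 = 0.75. A simulation with 12 per group, a true effect of 1.2 SD and 2,000 replicates agreed: 0.753 for that cell, 1.349 and 0.647 for the two extremes, and 0.993 to 0.999 where c = 0.

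The sign of c cannot be predicted. A treated patient who remembers the run-in as worse than it was inflates the effect. One whose memory drifts toward her current state shrinks it.

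**The case against.** The strongest reply is that late entry is conjecture. Patients are told to complete the diary daily (21.2). The form in 34.5 has a date on each page and a clock time for each movement, and the trial is double-blind. Informal review by staff is not ruled out. All of this stands, and it makes the bias a possibility rather than a finding. It does not close the gap: a date written by the patient does not show when the entry was made, blinding does not hide a felt effect, and no locking or copying is described.

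The reach is also limited. The primary endpoint is scintigraphic, and its intent-to-treat analysis does not use the diary baseline.

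A reader might infer three stronger claims. The documents do not support them.

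- *That the diary could show a randomized patient to be ineligible.* Inclusion 2 asks for "less than three complete spontaneous bowel movements per week with two or more of the following", but as a history over the previous three months, and the Visit 1 text gives the means of confirmation: "The Long Bowel Disease Questionnaire (BDQ) will be completed to confirm patients have functional constipation". A diary of 7 to 14 days begun after that visit cannot refute a three-month history. The earlier study A3309-001 used a different rule, "no more than 5 spontaneous complete bowel movements (SCBMs) during the 14 days preceding randomization", with its own 14-day screening period; the difference is not a defect here. No rate of conflicting diaries can be derived from the documents.
- *That adverse events and other medication go unseen until Visit 7.* Patients are asked about both at every visit (21.4).
- *That an earlier look would rescue missed home doses.* Visit 4 is dosing day 12, after all eleven home doses, so a review then could correct none of them. The last three doses are given by unit nurses and recorded by the unit (19.2, 19.3).

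**Conclusion.** The point holds as a low-cost improvement to data handling. The baseline for the diary-based secondary endpoints is not secured before treatment and stays open for about 20 to 23 days after randomization, assuming the first dose on the day of Visit 3. Over the assumed ranges (slope 0.3 to 0.7, shift up to half the effect in either direction) the adjusted effect would lie between 0.65 and 1.35 times the truth. It is unbiased if no differential late entry occurs. These multiples show sensitivity and do not predict what will happen. Loss of the baseline record is a separate risk that needs no assumption about patient behavior after dosing. The primary intent-to-treat result is not affected through this covariate.

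**What to change.** In 11.2, 11.3, 21.2 and 34.1:

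- At Visit 3, before the first dose, review the run-in pages for completeness, resolve or mark any blank days, and collect the pages (or copy and date them).
- Issue or continue a separate diary for treatment and follow-up.

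In 24.6, state that the Visit 3 version supplies the run-in covariate.

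Optionally, copy and date the treatment pages at Visit 6, for completeness and for the compliance record. They should be copied and not taken away: Visit 6 is the morning of day 14, and collection then would cut off the rest of that day's entries. The remaining pages come in at Visit 7 as now.

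The cost is a few minutes of coordinator time at visits that already take place, plus the schedule wording. Sample size, endpoints and visit count do not change.

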21.3 Laboratory safety assessments

Blood and urine samples will be obtained for the standard laboratory tests safety assessments of CBC, CMP, coagulation studies and UA at Visit 1, Visit 6 and Visit 7. A urine screen for drugs of abuse will be performed at Visit 1. These laboratory panels are further described in Appendix 3. The total amount of blood drawn will be approximately 20 mL on each visit for a total of 60 mL. Urine pregnancy tests will be performed for females of child bearing potential at Visit 1 and within 48 hours prior to the receipt of Albireo

34(89)

07 June 2010

radiation for both the abbreviated and full transit scintigraphy tests performed at Visit 2 and Visit 4, respectively. The laboratory analysis will be performed at Mayo Clinic.

21.4 Clinical safety assessments

A physical examination will be performed at the Visit 1 study entry and Visit 7 study completion and if necessary throughout the study.

Vital signs (including temperature, pulse, blood pressure and respiration rate) will be recorded at all visits.

Patients will be interviewed about adverse events and concomitant medications at every visit.

22 ADVERSE EVENTS

22.1 Definitions

Adverse Events (AE)

Any untoward medical occurrence in a patient or clinical investigation subject administered a pharmaceutical product and which does not necessarily have to have a causal relationship with this treatment. AE can therefore be any unfavorable and unintended sign (including e.g. an abnormal laboratory finding), symptom or disease temporally associated with the use of a medicinal product, whether or not considered related to the product.

Serious Adverse Event (SAE)

Any untoward medical occurrence or effect that at any dose

- results in death
- is life-threatening
- requires patient's hospitalization or prolongation of existing hospitalization
- results in persistent or significant disability or incapacity
- is a congenital anomaly/birth defect
- is regarded as medically important without meeting the above mentioned criteria.

The term life-threatening in the definition of "serious" refers to an event in which the subject was at risk of death at the time of the event; it does not refer to an event which hypothetically might have caused death if it was more severe.

Hospitalization is defined as an unplanned overnight stay. Note however that the subject must be formally admitted. Waiting in outpatient clinic or emergency room would not count. A planned hospital stay does not count as SAE, nor does staying in hospital for social reasons (e.g. respite care, the fact that there is noone at home to care for the patient).

Unexpected Adverse Drug experience

Any adverse drug experience, the specificity or severity of which is not consistent with the current Investigator Brochure (IB); or, if an IB is not required or available, the specificity or severity of which is not consistent with the risk information described in the general investigational plan or elsewhere in the current application, as amended.

Intensity

Mild means awareness of symptoms or signs, but easily tolerated (acceptable)

Moderate means discomfort enough to interfere with usual activity (disturbing)

Severe means incapacity to work or to do usual activity (unacceptable)

Causality

Certain - A clinical event, including laboratory test abnormality, occurring in a plausible time relationship to drug administration, and which cannot be explained by concurrent disease or other drugs or chemicals. The response to withdrawal of the drug (dechallenge) should be clinically plausible. The event must be definitive pharmacologically or phenomenologically, using a satisfactory rechallenge procedure if necessary.

Probable - A clinical event - including laboratory test abnormality - with a reasonable time sequence to use of the product, unlikely to be attributed to concurrent disease or other drugs or chemicals, and which follows a clinically reasonable response on withdrawal (dechallenge). Rechallenge information is not required.

Possible - A clinical event - including laboratory test abnormality - with a reasonable time sequence to use of the product, but which could also be explained by concurrent disease or other drugs or chemicals. Information on drug withdrawal may be lacking or unclear.

Unlikely - A clinical event - including laboratory test abnormality - with a temporal relationship with use of the product which makes a causal relationship improbable, and in which other drugs, chemicals or underlying disease provide plausible explanations.

Not related - Evidence exists that the AE has an etiology other than the study drug (e.g., pre-existing condition, underlying disease, intercurrent illness, or concomitant medication).

An adverse event will be considered associated with the use of a study drug if the attribution is certain, probable or possible.

